11.3.2 Statistical Methods

Clinical laboratory tests will be summarized at each visit during the Treatment Period. The baseline value will be the last measurement on or before the day of the first dose of study drug. This same baseline value will be used for all change from baseline tables in the Treatment Period and Post-Treatment Periods.

Mean changes from baseline to each post-baseline visit, including applicable post treatment visits, will be summarized for each treatment arm each protocol-specified laboratory parameter with the baseline mean, visit mean, change from baseline mean, standard deviation, and median.

Laboratory data values will be categorized as low, normal, or high based on normal ranges of the laboratory used in this study. Shift tables from baseline to minimum value, maximum value, and final values during the Treatment Period (Study Drug End Day \leq 2) will be created for each treatment arm. The shift tables will cross tabulate the frequency of subjects with baseline values below/within/above the normal range versus minimum/maximum/final values below/within/above the normal range.

The number and percentage of subjects with post-baseline values during the Treatment Periods meeting the specified criteria for Potentially Clinically Significant (PCS) laboratory values (defined in [Table 10](#) and [Table 11](#)) will be summarized for each treatment arm. A post-baseline value must be more extreme than the baseline value to be considered a PCS finding. A separate listing will be provided that presents all lab values for the subjects meeting PCS criteria during treatment.

For hemoglobin and the liver function tests (LFTs) of alkaline phosphatase, and total bilirubin, the number and percentage of subjects with a maximum Common Terminology Criteria for Adverse Events (CTCAE) Grade of 1, 2, 3, or 4 (see definitions in [Table 12](#)) at any post-baseline visit (regardless of the baseline value) through the end of treatment (i.e., Final Treatment Value) will be summarized for each treatment arm. All LFT tables will include summary rows for the number and percentage of subjects with at least Grade 2 and at least Grade 3 laboratory abnormalities. The hemoglobin table will include a summary row for the number and percentage of subjects with at least a Grade 2 laboratory abnormality.

For the liver function tests (LFTs) of ALT and AST, the number and percentage of subjects in with a maximum CTCAE Grade of 1, 2, 3, or 4 (see definitions in [Table 12](#)) at any post-nadir visit (regardless of the baseline value) through the end of treatment (i.e., Final Treatment Value) will be summarized for each treatment arm. Note, for these analyses, the nadir is used for reference instead of baseline. Both ALT and AST tables will include summary rows for the number and percentage of subjects with at least Grade 2 and at least Grade 3 laboratory abnormalities.

Accompanying listings of all ALT, AST, total, indirect and direct bilirubin, and alkaline phosphatase will be created for any subject who had at least a Grade 3 ALT, AST, alkaline phosphatase, or total bilirubin. A listing of the hematology results will be provided for subjects with at least Grade 2 hemoglobin abnormalities.

Table 12. Definitions of CTCAE Grades 1, 2, 3, and 4

Test	Grade 1	Grade 2	Grade 3	Grade 4
ALT/SGPT	> ULN – 3 × ULN	> 3 – 5 × ULN	> 5 – 20 × ULN	> 20 × ULN
AST/SGOT	> ULN – 3 × ULN	> 3 – 5 × ULN	> 5 – 20 × ULN	> 20 × ULN
Alkaline Phosphatase	> ULN – 2.5 × ULN	> 2.5 – 5 × ULN	> 5 – 20 × ULN	> 20 × ULN
Total Bilirubin	> ULN – 1.5 × ULN	> 1.5 – 3 × ULN	> 3 – 10 × ULN	> 10 × ULN
Hemoglobin Decreased	< LLN – 100 g/L	< 100 – 80 g/L	< 80 – 65 g/L	< 65 g/L

The number and percentage of subjects in each treatment arm with maximum on treatment lab values meeting the following criteria will be summarized:

- Post nadir ALT $\geq 3 \times$ ULN and post baseline total bilirubin value $\geq 2 \times$ ULN;
- Post nadir ALT $> 5 \times$ ULN (equivalent to Grade 3 or higher) and post baseline total bilirubin value $< 2 \times$ ULN.

A subject or event will be counted if the post-nadir ALT or AST laboratory values meet the above criteria regardless of the baseline laboratory value (i.e., the post nadir laboratory value does not need to be worse than the baseline laboratory value). The maximum ratio relative to the ULN will be used to determine if subjects meet the criteria listed above.

For subjects meeting the ALT $\geq 3 \times$ ULN and total bilirubin value $\geq 2 \times$ ULN criterion during the Treatment Period, a corresponding listing of all ALT, AST, alkaline phosphatase, and total, direct, and indirect bilirubin values will be provided.

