A 12-lead resting ECG will be obtained at visits specified in [Table 4](#) (or as clinically needed). The ECG will be obtained prior to the blood collection.

ECGs will be recorded after the subject has been supine for at least 5 minutes. Subjects should be instructed to remain completely stationary during the ECG recording (approximately 10 seconds), with no talking, laughing, deep breathing, sleeping, or swallowing.

The ECGs will be evaluated by an appropriately trained physician at the site ("local reader"). The local reader from the site will interpret, sign, and date all ECG tracings and will provide his/her global interpretation as a written commitment on the tracing using the following categories:

- Normal ECG
- Abnormal ECG – not clinically significant
- Abnormal ECG – clinically significant

Only the local reader's evaluation of the ECG will be collected and documented in the subject's source. The automatic machine reading (i.e., machine-generated measurements

and interpretation that are automatically printed on the ECG tracing) will not be collected. The QT interval measurement (corrected by Fridericia's formula, QTcF) will be documented in the eCRF only if the local reader selects "prolonged QT" on the eCRF.

The original ECG tracing will be retained in the subject's record at the study site.

Clinical Laboratory Tests

Samples will be obtained at a minimum for the clinical laboratory tests outlined in [Table 6](#) at the visits specified in [Table 4](#) and [Table 5](#). Blood samples for serum chemistry tests should ideally be collected following a minimum 8-hour fast (with the exception of the Screening Visit, which may be done non-fasting). Subjects whose visits occur prior to the morning dose of study drugs should be instructed to fast after midnight. Subjects whose visits occur following the morning dose of study drugs should be instructed to fast after breakfast until the study visit occurs. Blood samples should still be drawn if the subject did not fast for at least 8 hours. Fasting status will be recorded in the source documents and on the laboratory requisition. The baseline laboratory test results for clinical assessment for a particular test will be defined as the last measurement prior to the initial dose of study drugs.

A central laboratory will be utilized to process and provide results for the clinical laboratory tests.

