CREATININE	1.5 – 1.7 mg/dL	1.8 – 2.0 mg/dL	2.1 – 2.5 mg/dL	>2.5 mg/dL or requires dialysis
GLUCOSE, SERUM, LOW	<LLN – 55 mg/dL <LLN – 3.0 mmol/L	<55 – 40 mg/dL <3.0 – 2.2 mmol/L	<40 – 30 mg/dL <2.2 – 1.7 mmol/L	<30 mg/dL <1.7 mmol/L
GLUCOSE, SERUM, HIGH (Fasting)	>ULN – 160 mg/dL >ULN – 8.9 mmol/L	>160 – 250 mg/dL >8.9 – 13.9 mmol/L	>250 – 500 mg/dL >13.9 – 27.8 mmol/L	>500 mg/dL >27.8 mmol/L or acidosis
MAGNESIUM, SERUM, LOW	<LLN – 1.2 mg/dL <LLN – 0.5 mmol/L	<1.2 – 0.9 mg/dL <0.5 – 0.4 mmol/L	<0.9 – 0.7 mg/dL <0.4 – 0.3 mmol/L	<0.7 mg/dL <0.3 mmol/L
MAGNESIUM, SERUM, HIGH	>ULN – 3.0 mg/dL >ULN – 1.23 mmol/L		>3.0 – 8.0 mg/dL >1.23 – 3.30 mmol/L	>8.0 mg/dL >3.30 mmol/L
PHOSPHATE, SERUM, LOW	<LLN – 2.5 mg/dL <LLN – 0.8 mmol/L	<2.5 – 2.0 mg/dL <0.8 – 0.6 mmol/L	<2.0 – 1.0 mg/dL <0.6 – 0.3 mmol/L	<1.0 mg/dL <0.3 mmol/L
POTASSIUM, SERUM, LOW	<LLN – 3.0 mmol/L		<3.0 – 2.5 mmol/L	<2.5 mmol/L
POTASSIUM, SERUM, HIGH	>ULN – 5.5 mmol/L	>5.5 – 6.0 mmol/L	>6.0 – 7.0 mmol/L	>7.0 mmol/L
PROTEIN, SERUM, LOW	5.5 – 6.0 g/dL	<5.5 – 5.0 g/dL	<5.0 g/dL	
SODIUM, SERUM, LOW	<LLN – 130 mmol/L		<130 – 120 mmol/L	<120 mmol/L
SODIUM, SERUM, HIGH	>ULN – 150 mmol/L	>150 – 155 mmol/L	>155 – 160 mmol/L Hospitalization may be indicated	>160 mmol/L
TRIGLYCERIDES HIGH (fasting)	150-300 mg/dL; 1.71 – 3.42 mmol/L	>300-500 mg/dL; >3.42-5.7 mmol/L	>500-1000 mg/dL; >5.7 – 11.4 mmol/L	>1000 mg/dL; >11.4 mmol/L
URIC ACID, SERUM, HIGH	7.5 – 10.0 mg/dL	10.1-12.0 mg/dL	12.1-15.0 mg/dL	>15.0 mg/dL

Clinical Toxicity Grades for HCV Studies
v1.1; 08 June 2009

Clinical Toxicity Grades for HCV Studies (Continued)				
	GRADE 1 TOXICITY	GRADE 2 TOXICITY	GRADE 3 TOXICITY	GRADE 4 TOXICITY
ENZYME				
ALT/SGPT	>ULN - 3.0 × ULN	>3.0 - 5.0 × ULN;	>5.0 - 20.0 × ULN	>20.0 × ULN
AST/SGOT	>ULN - 3.0 × ULN	>3.0 - 5.0 × ULN;	>5.0 - 20.0 × ULN	>20.0 × ULN
ALKALINE PHOSPHATASE	>ULN - 2.5 × ULN	>2.5 - 5.0 × ULN	>5.0 - 20.0 × ULN	>20.0 × ULN
AMYLASE	>ULN - 1.5 × ULN	>1.5 - 2.0 × ULN	>2.0 - 5.0 × ULN	>5.0 × ULN
LIPASE	>ULN - 1.5 × ULN	>1.5 - 2.0 × ULN	>2.0 - 5.0 × ULN	>5.0 × ULN

1 Adapted from the National Cancer Institute's Common Terminology Criteria for Adverse Events v4.0 (CTCAE)

2 Used for all HCV development compounds

Document Approval

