7.1 Demographic and Baseline Characteristics

Demographics include age, weight, and BMI as continuous variables, and sex, race, ethnicity, age category ($[< 55 \text{ years or } \geq 55 \text{ years}]$ and $[< 65 \text{ or } \geq 65 \text{ years}]$), birth year (< 1945 , 1945 to 1965 , > 1965), country (Canada, New Zealand, Australia, and United Kingdom), and BMI category ($< 30 \text{ kg/m}^2$ or $\geq 30 \text{ kg/m}^2$).

Baseline characteristics will include: IL28B genotype ([CC, CT, or TT] and [CC or non-CC]), prior treatment history (treatment naïve, pegIFN/RBV null-responder, pegIFN/RBV partial responder, SOF breakthrough/nonresponder, HCV therapy relapser, HCV relapse/breakthrough, HCV therapy nonresponder, pegIFN intolerant, and pegIFN experienced), baseline HCV RNA levels ([continuous (use \log_{10} HCV RNA)] and [$< 800,000 \text{ IU/mL}$ or $\geq 800,000 \text{ IU/mL}$]), baseline HOMA-IR (< 3 or $\geq 3 \text{ mU} \times \text{mmol/L}^2$), baseline IP-10 category (< 600 or $\geq 600 \text{ ng/L}$), baseline albumin (continuous), baseline albumin (< 35 , $\geq 35 \text{ g/L}$), baseline platelet count (continuous, and $< 90 \times 10^9/\text{L}$, $\geq 90 \times 10^9/\text{L}$), baseline alpha fetoprotein (continuous, and $< 20 \text{ ng/mL}$, $\geq 20 \text{ ng/mL}$), baseline fibrosis stage (equivalent to Metavir F0 – F1, F2, F3, or F4), Child Pugh score (5, 6, or > 6), FibroTest Score, tobacco (user, ex-user, or non-user) and alcohol (drinker, ex-drinker, or non-drinker) use status, history of diabetes, history of depression or bipolar disorder, history of hypertension, and history of cardiovascular disease other than hypertension.

HOMA-IR is defined as $\text{fasting glucose (mmol/L)} \times \text{fasting insulin (\muIU/mL)} \div 22.5$. Subjects who do not have concurrent fasting glucose and fasting insulin values at baseline will be excluded from the summary of baseline HOMA-IR.

Baseline Child-Pugh score is determined by the Day 1 assessment of ascites and hepatic encephalopathy along with the baseline values of total bilirubin, serum albumin, and international normalized ratio (INR). The Child-Pugh score is the sum of the point assigned for each of the five observed findings as defined in [Table 8](#).

Table 8. Child-Pugh Classification of Severity of Cirrhosis

Parameter	Points Assigned for Observed Findings		
	1	2	3
Total bilirubin, $\mu\text{mol/L}$ (mg/dL)	$< 34.2 (< 2)$	$34.2 – 51.3 (2 – 3)$	$> 51.3 (> 3)$

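### Glucose and triglyceride changes and high PCS counts ignore fasting status, so within-arm changes at most on-treatment visits can mix a meal effect with a drug effect

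*SAP*

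**What the plan says.** **Sampling rules (Protocol 5.3.1.1, Clinical Laboratory Tests).** Serum chemistry samples "should ideally be collected following a minimum 8-hour fast (with the exception of the Screening Visit, which may be done non-fasting"). Two instructions depend on when the visit falls:

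- For a visit ahead of the morning dose, the subject is told to take nothing from midnight onward.
- For a visit held later than that dose, the wording is: "Subjects whose visits occur following the morning dose of study drugs should be instructed to fast after breakfast until the study visit occurs".

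Unfasted samples are not discarded: "Blood samples should still be drawn if the subject did not fast for at least 8 hours". The protocol also has fasting status noted in the source records and on the form sent to the laboratory.

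**Timing of dose and visit.** Protocol 5.5.1 has the direct-acting antivirals taken every morning, and 5.3.1.2 requires food with them. Table 4, note b, places all Day 1 procedures before the first dose. Table 4, note m, and 5.3.2.1 give Week 2 a pre-dose pharmacokinetic sample and on-site dosing.

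**Analysis (SAP).** Section 11.3.2 states: "Mean changes from baseline to each post-baseline visit, including applicable post treatment visits, will be summarized for each treatment arm". Baseline is the last measurement up to the first dosing day. PCS counts use the limits in Table 11. Section 11.3 brings in local and SAE-driven laboratory values. None of these rules mentions fasting. The SAP uses fasting status once, in 7.1: "Subjects who do not have concurrent fasting glucose and fasting insulin values at baseline will be excluded from the summary of baseline HOMA-IR".

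**Grading (Protocol Appendix C).** The high triglyceride row is headed "TRIGLYCERIDES HIGH (fasting"), and the high glucose row carries the same label.

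**The concern.** Glucose and triglycerides are the chemistry values for which the protocol's own grading specifies a fasting sample. The visit instructions make fasting more likely at baseline than at a later visit held after the morning dose. If the two samples in a change score differ in this way, the mean change reflects the meal as well as the drug. A post-meal value can also cross a limit that was set for fasting samples.

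The stake is limited to safety reporting, but the trial has no untreated control group (Protocol 5.6.1). Change from baseline within an arm is therefore how a laboratory signal would be read, and no placebo change is available to show what meals alone would do. The arms are also small: one subject is 1/10 = 10 percentage points of a 10-subject arm, or 1/20 = 5 points of Arm E.

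**Working it through.** The documents state no figure on this point, so there is none to reproduce. The check has three steps.

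**1. Which visits differ from baseline by instruction?**

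| Visit | Relation to the morning dose | Instruction that applies |
|---|---|---|
| Day 1 (usual baseline) | Before | Fast from midnight |
| Week 2 | Starts before (pre-dose sample, on-site dosing) | Fast from midnight |
| Weeks 1, 4, 8, 10, 12 | Not fixed; may be after | If after, fast from breakfast only |
| Post-treatment Weeks 4 and 12 | No study dose is taken | Neither instruction clearly applies |
| Screening (fallback baseline) | No study dose is taken | May be non-fasting |

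A fast from breakfast reaches 8 hours only if the visit is at least 8 hours later. As an example with an assumed time, breakfast at 08:00 requires a visit at 16:00 or later. The documents give no visit times.

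**2. Are the Table 11 limits the fasting limits?**

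| Test | SAP Table 11, very high | Appendix C, lower bound of Grade 3 | Label in Appendix C |
|---|---|---|---|
| Glucose | > 250 mg/dL (> 13.9 mmol/L) | > 250 mg/dL (> 13.9 mmol/L) | Fasting |
| Triglycerides | > 500 mg/dL (> 5.7 mmol/L) | > 500 mg/dL (> 5.7 mmol/L) | Fasting |

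They match in both units. Table 11 does not carry the label.

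**3. What would pooling do to a mean change?** Let f_v be the non-fasting share at the visit, f_b the non-fasting share at baseline, and m the mean increment due to a meal. Then

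bias in mean change = (f_v − f_b) × m.

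All three inputs are assumptions. The ranges used for m are 10 to 40 mg/dL for glucose and 20 to 60 mg/dL for triglycerides.

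| f_b | f_v | Glucose, mg/dL | Triglycerides, mg/dL |
|---|---|---|---|
| 0 | 0.25 | 0.25 × 10 to 0.25 × 40 = +2.5 to +10 | 0.25 × 20 to 0.25 × 60 = +5 to +15 |
| 0 | 0.75 | 0.75 × 10 to 0.75 × 40 = +7.5 to +30 | 0.75 × 20 to 0.75 × 60 = +15 to +45 |
| 0.25 | 0.25 | 0 | 0 |
| 0.25 | 0 | −0.25 × 10 to −0.25 × 40 = −2.5 to −10 | −0.25 × 20 to −0.25 × 60 = −5 to −15 |

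The table shows how the bias behaves and does not estimate it. The sign follows f_v − f_b. The instructions make a positive difference the likelier case, but they do not guarantee it. When both samples of every pair are fasting, f_v = f_b = 0 and the term vanishes.

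**The case against.** The best case for leaving the plan alone has five parts.

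- **Direction.** The 8-hour fast is the preferred condition at every visit except Screening, a late visit can meet it even after breakfast, and samples are kept regardless on Day 1 too. If the Day 1 value is missing, a possibly non-fasting Screening value becomes the baseline and pushes the change downward. This stands as a limit: upward is the likely direction and is not certain.
- **Coverage.** Week 2 is fasting by instruction, and the dose-based wording does not clearly apply after treatment. This stands, and it confines the point to the other on-treatment visits.
- **PCS.** Table 11 never calls its limits fasting, and Appendix C serves toxicity management. A flagged value must also be worse than baseline, all values of flagged subjects are listed, and subjects with HbA1c above 8.5% are excluded. These features make a misleading count rarer and easier to spot. They do not help a reader of the table, who cannot tell fasting from post-meal values. The worse-than-baseline condition gives little protection when the baseline is fasting.
- **Sparse data.** With 25% to 75% of visit samples unfasted (assumed) and a fully fasting baseline, a 10-subject arm keeps about 10 × 0.75 = 7.5 down to 10 × 0.25 = 2.5 fasting pairs. This is a good reason not to replace the all-sample tables. It does not rule out adding to them.
- **Arms C to F.** The protocol supplied describes only Arms A and B, while the SAP covers six arms. Whether the same visit instructions apply to the other four cannot be seen.

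**Conclusion.** The point holds as a minor gap in safety reporting. SAP 11.3.2 summarises glucose and triglyceride changes and high PCS counts without regard to fasting status. The visit instructions favour a fasting baseline over a fasting later sample, and the high limits are ones that the protocol labels as fasting. Within-arm changes at Weeks 1, 4, 8, 10 and 12 can therefore include a meal effect, most likely upward. This assumes that some of those visits are held within 8 hours of breakfast, which the instructions allow.

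A reader might infer three stronger conclusions, and the documents support none of them:

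- **A known upward bias, such as 5 to 45 mg/dL for triglycerides.** Every input to such a figure is assumed, and other inputs that are equally undocumented give zero or a negative value.
- **A bias in every arm and at every later visit.** Week 2 does not share the asymmetry, post-treatment visits have no clear instruction, and the protocol text for Arms C to F is not available.
- **A distorted treatment comparison or efficacy result.** Arms A and B follow the same sampling rules, so their contrast is not systematically affected. SVR12 does not depend on these values.

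**What to change.** Amend SAP 11.3.2 before the tables are produced:

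1. Keep the all-sample tables as planned.
2. Add change-from-baseline summaries of glucose and triglycerides, by arm and visit, limited to pairs in which both the baseline and the visit sample are recorded as fasting. Show the number of pairs.
3. Present the high glucose and high triglyceride PCS counts by fasting status of the sample: fasting, non-fasting or unknown.

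No new data collection is called for, because the protocol already has fasting status recorded and the SAP relies on it for baseline HOMA-IR. The status must be carried from the requisition into the analysis data for post-baseline samples as well. The cost is SAP wording and two small extra tables. Some 10-subject arms may have few fasting pairs, and local or SAE-driven values may fall into the unknown category.

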6.7.5 Management of ALT Elevations

Transient asymptomatic Grade 3 – 4 ALT elevations have been observed in approximately 1% of subjects receiving ABT-450/r-containing regimens. If a subject experiences a post-baseline increase in ALT to $> 5 \times$ ULN that is increased from a previous measurement, the subject should have a confirmatory ALT measurement performed.

If the ALT increase is confirmed to be $> 5 \times$ ULN and increased from the previous measurement, the recommendations below should be followed:

- Evaluate for alternative etiology of ALT elevation: update medical history and concomitant medications eCRF (if applicable), and obtain additional testing as appropriate.
- Manage the subject as medically appropriate.
- Repeat ALT, AST, total and fractionated bilirubin, alkaline phosphatase, and INR within 1 week. Repeat liver chemistries as indicated until resolution.
- Discontinue study drugs if any of the following is observed at any time:
 - ALT level is $\geq 20 \times$ ULN.
 - Increasing direct bilirubin, increasing INR, or onset of symptoms/signs of hepatitis.

Alternate management of ALT increases is permitted with approval of the AbbVie Study Designated Physician.

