6.1.2 Study Days

Study days (days relative to the first dose of study drug) are calculated for each time point relative to the first dose of study drug. Study Days are negative values when the time point of interest is prior to the first study drug dose day. Study Days are positive values when the time point of interest is after the first study drug dose day. There is no Study Day 0. Study Day 1 is the day of the first dose of study drug.

Study Drug End Days

For all subjects who receive at least one dose of study drug, study drug end days (days relative to the last dose of study drug) are calculated relative to the last dose of study drug. The last day of study drug is defined as Study Drug End Day 0. Days before it have negative study drug end days and days after it have positive study drug end days.

Final Treatment Value

The final treatment value for each subject is the last non-missing measurement collected after Study Day 1 and on or before Study Drug End Day 2.

Final Post-Treatment Value

The final post-treatment value for each subject is the last non-missing measurement collected after Study Drug End Day 2, and on or before Study Drug End Day 999.

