Note: Data must also have Study Drug End Day ≤ 2 for all windows. The result closest to the scheduled time point will be used. Child-Pugh classification (for cirrhotic subjects only), FibroTest are collected at Screening and Week 12 (or upon study discontinuation) and will use those visit windows as defined above. FibroTest is also collected at baseline, only if not performed at the time of screening.

Table 3. Analysis Time Windows for HCV RNA, Resistance Endpoints, Laboratory Data, and Vital Sign (Treatment Period) for 8-Week of Treatment

Scheduled Visit	Nominal Day (Study Day)	Time Window (Study Day Range)
Day 1/Baseline ^a	1 ^a	≤ 1 ^a
Week 1	7	2 to 10
Week 2	14	11 to 21
Week 4	28	22 to 42
Week 8	56	43 to 70
Final Treatment Visit ^b		2 to ≤ 2 days after last dose of study drug

a. Day of first dose of study drug.

b. The last value within the window will be used to define the Final Treatment visit value. The upper bound of this Final window is Study Drug End Day ≤ 2.

Note: Data must also have Study Drug End Day ≤ 2 for all windows. The result closest to the scheduled time point will be used.

Table 4. Analysis Time Windows for HCV RNA, Resistance Endpoints, Laboratory Data, and Vital Sign (Treatment Period) for 6-Week of Treatment

Scheduled Visit	Nominal Day (Study Day)	Time Window (Study Day Range)
Day 1/Baseline ^a	1 ^a	≤ 1 ^a
Week 1	7	2 to 10
Week 2	14	11 to 21
Week 4	28	22 to 35
Week 6	42	36 to 49
Final Treatment Visit ^b		2 to ≤ 2 days after last dose of study drug

a. Day of first dose of study drug.

b. The last value within the window will be used to define the Final Treatment visit value. The upper bound of this Final window is Study Drug End Day ≤ 2.

Note: Data must also have Study Drug End Day ≤ 2 for all windows. The result closest to the scheduled time point will be used.

Table 5. Analysis Time Windows for HCV RNA, Resistance Endpoints, (Post-Treatment Period)

Scheduled Visit ^a	Nominal Day (Study Drug End Day)	Time Window (Study Drug End Day Range)
Post-Treatment Week 2	14	3 to 21
Post-Treatment Week 4	28	22 to 42
Post-Treatment Week 8	56	43 to 77
Post-Treatment Week 12	84	78 to 126
Post-Treatment Week 24	168	127 to 210
Post-Treatment Week 36	252	211 to 294
Post-Treatment Week 48	336	295 to 378
SVR ₄ ^b	28	3 to 56
SVR ₁₂ ^b	84	57 to 126
SVR ₂₄ ^b	168	127 to 210

a. Post-Treatment Visits are applicable for subjects who received at least one dose of study drug.

b. For SVR windows, the last value in the window will be used.

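### The SAP's liver grades and ALT-plus-bilirubin rows stop at Study Drug End Day 2, so a subject whose bilirubin first reaches 2 × ULN after a liver-related stop is missed by the combined count

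*SAP*

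**What the plan says.** **Liver grades (SAP 11.3.2).** For ALT and AST, subjects with a maximum CTCAE grade "at any post-nadir visit (regardless of the baseline value) through the end of treatment (i.e., Final Treatment Value) will be summarized". For alkaline phosphatase and total bilirubin, the count is of subjects with a maximum grade "at any post-baseline visit (regardless of the baseline value) through the end of treatment (i.e., Final Treatment Value) will be summarized". SAP 6.1.2 defines the Final Treatment Value as the "last non-missing measurement collected after Study Day 1 and on or before Study Drug End Day 2".

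**Combined rows (SAP 11.3.2).** "The number and percentage of subjects in each treatment arm with maximum on treatment lab values meeting the following criteria will be summarized". The first criterion is post-nadir ALT ≥ 3 × ULN with total bilirubin ≥ 2 × ULN. The second is post-nadir ALT > 5 × ULN with total bilirubin < 2 × ULN. For subjects meeting the first criterion "during the Treatment Period, a corresponding listing of all ALT, AST, alkaline phosphatase, and total, direct, and indirect bilirubin values will be provided".

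**Windows (SAP 6.2).** The notes to the treatment-period tables say: "Data must also have Study Drug End Day ≤ 2 for all windows".

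**Other liver output (SAP 11.3.2).** The provision for the liver listing begins: "Accompanying listings of all ALT, AST, total, indirect and direct bilirubin, and alkaline phosphatase will be created for any subject who had at least". The threshold it then sets is Grade 3 in any of the four graded liver tests. No end day is given for that listing. A further listing shows all laboratory values for subjects who meet the potentially clinically significant (PCS) criteria during treatment.

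**Protocol 6.7.5.** After a confirmed ALT > 5 × ULN that has risen from the previous value, liver tests are repeated within a week and then until resolution. Study drugs stop for ALT ≥ 20 × ULN, or for: "Increasing direct bilirubin, increasing INR, or onset of symptoms/signs of hepatitis".

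**The concern.** The adverse event and laboratory windows differ. SAP 11.2.1 counts adverse events as treatment-emergent through 30 days after the last dose, while the liver grades and combined rows end at Day 2. The subjects for whom this matters are those who stop drug because of a liver finding. Their liver tests are most likely to keep changing after the stop, and protocol 6.7.5 orders further tests in them.

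None of the 6.7.5 stopping triggers requires total bilirubin to have reached 2 × ULN. A subject can stop below that level and cross it later, and the crossing then falls outside the combined row. That row is the SAP's summary count of joint ALT and bilirubin elevation. The regimen contains a protease inhibitor with known ALT rises, and protocol 3.2 says the combination has not previously been given to HCV-infected subjects. In arms of 10 or 20, one subject is a visible share of the table.

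**Working it through.** The plan gives no figure on this point, so there is nothing to reproduce. The check has two parts: following the definitions, and bounding the number of subjects.

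**1. The definitions applied to one subject (hypothetical values).** ALT is 22 × ULN and bilirubin 1.7 × ULN at the last dose, and drug stops because ALT is ≥ 20 × ULN. Bilirubin is then 2.6 × ULN on Study Drug End Day 7 and 3.4 × ULN on Day 14.

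| Cut-off | Max ALT | Max bilirubin | Row | Bilirubin grade (SAP Table 12) |
|---|---|---|---|---|
| Day 2 (as planned) | 22 × ULN | 1.7 × ULN | ALT > 5, bilirubin < 2 | 2 |
| Day 30 or Day 42 | 22 × ULN | 3.4 × ULN | ALT ≥ 3, bilirubin ≥ 2 | 3 |

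For such a subject the Day 2 limit can only keep them out of the combined row. It is explicit for the grade tables. For the two rows it follows from their on-treatment wording, the SAP 6.2 windows, and the same section's equation of the Treatment Period with Study Drug End Day ≤ 2 for the shift tables.

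**2. Ceiling on the number of subjects.** Affected subjects are a subset of those with ALT > 5 × ULN, so the expected number of the latter is a ceiling. Inputs from protocol 3.0, Table 2 (genotype 1, 3-DAA regimens):
- without RBV: 0.2%
- with RBV, no cirrhosis: 0.7% or 1.2%
- cirrhosis: 2.9% of 208 (12 weeks) and 0 of 172 (24 weeks)

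Protocol 6.7.5 also gives about 1% overall. Arm sizes from SAP 4.2:
- A + F = 20, without RBV
- B + C + D = 30, with RBV
- E = 20, with cirrhosis

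Pooled cirrhotic rate: 0.029 × 208 ≈ 6, and 6 / 380 = 1.58%, so Arm E contributes 20 × 0.0158 = 0.316. With 2.9% alone it contributes 0.58.

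- Pooled, RBV at 0.7%: 20 × 0.002 + 30 × 0.007 + 0.316 = 0.57
- Pooled, RBV at 1.2%: 0.04 + 0.36 + 0.316 = 0.72
- 2.9% in Arm E, RBV at 0.7%: 0.04 + 0.21 + 0.58 = 0.83
- 2.9% in Arm E, RBV at 1.2%: 0.04 + 0.36 + 0.58 = 0.98
- 1% in the 50 without cirrhosis, 2.9% in Arm E: 0.50 + 0.58 = 1.08

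The ceiling is therefore 0.57 to 1.08 subjects in 70.

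**3. Illustration for the affected subset.** The documents do not give the fraction f of these subjects who stop and first cross 2 × ULN after Day 2. As an assumption, let f run from 5% to 50%.
- Flat 1% in all 70: expected 0.70f = 0.035 to 0.35. P(at least one) = 1 − (1 − 0.01f)^70 = 0.03 to 0.30.
- 1% in 50 and 2.9% in 20: expected 1.08f = 0.054 to 0.54. P(at least one) = 1 − (1 − 0.01f)^50 × (1 − 0.029f)^20 = 0.05 to 0.42.

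**4. Weight of one subject.** 1/10 = 10 percentage points in a 10-subject arm, and 1/20 = 5 points in Arm E.

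**5. Where to end a longer window.** The PT Week 4 laboratory window is Study Drug End Days 22 to 42 (SAP Table 7), which is 21 days. A Day 30 cut-off would drop Days 31 to 42, or 12 of the 21.

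**The case against.** The case for leaving the SAP alone is substantial.

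- **The rows are right as defined.** A reader might infer that the SAP misclassifies subjects or departs from the protocol. It does neither. The rows are defined on on-treatment maxima, and protocol 8.1.5.2 likewise restricts shifts and PCS values to treatment. This stands: the gap is in what is summarized.
- **The subject is not hidden.** A reader might infer that a serious liver case would be lost. The Grade 3 listing gives all liver values for anyone with ALT > 5 × ULN. The PCS listing usually adds the rest, since its ALT criterion also needs at least 2 × baseline. A laboratory value that forces stopping is recorded as an adverse event (protocol 5.3.1.1) and enters the discontinuation tables. This stands too, but a listing does not change the count in a table.
- **Timing.** A reader might count days in the one-week repeat period and infer that most repeats fall after Day 2. That requires drug to stop on the day ALT is confirmed. When the stop is for rising bilirubin, the value that triggers it is itself on treatment, and a discontinuation visit held within 2 days (protocol 5.4.1) is inside the window. No share of missed repeats can be supported.
- **Net bias is not shown.** The rows state no requirement that the ALT and bilirubin peaks coincide, so an unrelated early bilirubin rise can put a subject in the combined row. The late-crossing effect runs one way, but the row as a whole cannot be called biased downward.
- **The case is unlikely.** Protocol 3.0 reports bilirubin peaking by Weeks 1 and 2, ALT rises mostly in the first 4 weeks, and no hepatic dysfunction among related ALT cases.
- **The protocol supplied covers only Arms A and B.** That 6.7.5 governs Arms C to F, including cirrhotic Arm E, is an assumption.
- **Later values bring relapse-related ALT rises.** This stands as a cost of the fix.

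**Conclusion.** The point holds as a minor gap in the summary output. A subject stopped under protocol 6.7.5 (for example for ALT ≥ 20 × ULN, rising INR or symptoms) whose total bilirubin first reaches 2 × ULN after Study Drug End Day 2 would be absent from the combined row and its listing, and the maximum grade could be too low.

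About one subject or fewer with ALT > 5 × ULN is expected among 70, and only some unknown part of that number would be affected. This rests on 3-DAA genotype 1 rates carrying over to this regimen and these genotypes, and on 6.7.5 applying to all six arms. Efficacy results and the planned sample size do not depend on it. It is worth acting on because the change is cheap and one case is 5 to 10 percentage points of an arm.

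**What to change.** Keep every planned table, including the PCS and shift tables. In SAP 11.3.2:

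1. Add one supplementary ALT-plus-bilirubin count and a matching liver CTCAE-grade summary. Use all values, scheduled and unscheduled, from first dose through the PT Week 4 window (Study Drug End Day 42).
2. Add to the combined-criterion listing any subject who newly meets the criterion in that longer window.
3. Flag ALT rises that coincide with HCV RNA ≥ LLOQ.
4. State that the ALT nadir is the lowest value before the rise. The section does not say how the nadir is chosen, and a lower post-treatment ALT should not displace it.

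The cost is a few lines of SAP text and a re-run of existing programs with a longer window. The data are already collected: 6.7.5 orders the repeats, PT Week 4 has a scheduled chemistry panel, and SAP 11.3 already admits central and local laboratory results. The downside is that a few relapse-related ALT rises may enter the supplementary count. The HCV RNA flag identifies them, and the on-treatment tables remain unaffected.
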